8.1. Specification of safety parameters

Safety measurements performed during the study are indicated in [Table \(4.1.2\) 1](#).

Safety assessment of lyophilized S95014 will include:

- adverse events (AEs) assessments
- physical examinations, performance status ECOG (see [Appendix 2](#))
- laboratory assessments including haematology, blood biochemistry, coagulation parameters, urinalysis, hepatitis serology
- vital signs measurements

Adverse events will be collected regardless of grade or IMP relationship and will be graded according to current National Cancer Institute (NCI) CTCAE criteria 5.0

Any significant abnormality detected during safety assessments from the patient ICF signature until the withdrawal visit must be reported on the adequate eCRF page by the investigator at each visit (AE, medical history or sign & symptoms).

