Biochemistry	Albumin, Alkaline Phosphatase (ALP), ALT, AST, Ammonia, Bicarbonates, Gamma-glutamyl-transferase (GGT), Lactate dehydrogenase (LDH), Calcium, Phosphorus, Sodium, Potassium, Creatinine, Total Bilirubin, Total Cholesterol, LDL, HDL, Triglycerides, BUN or Urea, Uric Acid, Amylase, Lipase, Glucose
Urinary analysis	Macroscopic Panel (Dipstick) (Blood, Glucose, Ketones, Protein) If the dipstick test is at least 2+ on one or more parameter(s), quantitative urinary biochemistry tests will be performed on the abnormal parameter(s)
Blood coagulation	Prothrombin time - International Normalized Ratio (INR), fibrinogen, protein S activity, antithrombin activity, activated Partial Thromboplastin Time (aPTT), D-dimer, FDP
Hepatitis serology	HbsAg, HbsAb, HbcAb, if HbsAg or HbcAb positive check viral load (HBV-DNA) at baseline, HCV RNA-PCR, HEV RNA-PCR
Pregnancy Test	Pregnancy testing is mandatory at inclusion (serum), before each phase of the consolidation (i.e. S1, S2, S3) and at withdrawal visit (serum) for WOCBP

All samplings for biochemistry should be taken in fasting conditions.

Abnormal laboratory values or test/exams results (i.e. blood pressure recording) will constitute an AE if they are:

- associated with signs and symptoms, or
- deemed clinically significant in the investigator's opinion, or
- if they require curative therapies, or
- associated with delay of study medication, or
- associated with study discontinuation

Triplet ECG will be assessed at inclusion and at the withdrawal visit.

LVEF assessment will be performed through echocardiography or MUGA scan at inclusion and at the withdrawal visit.

Results of LVEF assessment and ECG performed in the frame of previous CL2-95014-002 study withdrawal visit can be used to assess patient's inclusion in order to avoid unnecessary exam

Post-withdrawal follow-up: After the withdrawal visit, a contact or telephone call will be done approximately 30 days after the last S95014 infusion, except in case of consent withdrawal. The following information will be collected:

- follow-up adverse events
- the first new anticancer treatment after withdrawal and its starting date.

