8.3. Definition of Adverse events

An adverse event is defined as any untoward medical occurrence in a subject participating in a clinical study, whether or not there is a causal relationship with the IMP and/or experimental procedures, occurring or detected from the date the participant signs the information and consent form, irrespective of the period of the study (periods without administration of the IMP (e.g. run-in period) are also concerned).

An adverse event can therefore be:

- any unfavourable and unintended sign (including an abnormal finding from an additional examination such as lab tests, X-rays, ECG, ...) which is deemed clinically relevant by the investigator,
- any symptom or disease,
- any worsening during the study of a symptom or a disease already present when the participant entered the study (increase in frequency and/or intensity), including the studied pathology,

and detected during a study visit or at an additional examination or occurred since the previous study visit (including relevant event reported in participant's diary or safety evaluation scale).

Of note:

Any hospitalisation for administration of anti-tumoral treatment and/or associated protocol (during or after the study) or other care measures for cancer (e.g. overnight hospital stay to receive a blood or platelets transfusion), for social reasons, educational purpose (e.g. learning of diabetes management by the participant) or routine check-up should not be considered as an adverse event and should not be reported in the e-CRF. The following procedures, whether planned before the study or not, whether leading to a hospitalisation or not, **should not be reported in the e-CRF and kept in the source data (or patient file):**

- therapeutic procedures related to a non-aggravated medical history (e.g. cataract extraction not due to an aggravation of the cataract during the study, haemodialysis sessions related to a renal insufficiency not aggravated during the study),
- prophylactic procedures (e.g. sterilisation, wisdom teeth removal),
- comfort procedures (e.g. cosmetic surgery),
- control procedures of a pre-existing condition without aggravation (e.g. colonoscopy to control the remission of colon cancer).

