8.8. Classification of an adverse event (seriousness, severity, causality, expectedness)

It is important that the investigator gives his/her own opinion regarding the **seriousness**, the **severity** of the event as well as the **cause-effect relationship** between an adverse event and the research (IMP or study protocol). This evaluation must be assessed by the investigator and reported in the AE form. In addition, the sponsor will be responsible for the evaluation the **expectedness** of the event (See [Section 8.9.3](#)).

The Seriousness should be evaluated according to international guidances (see definition [Section 8.4](#), in accordance with [ICH Topic E2A](#) and [DIRECTIVE 2001/20/EC OF THE EUROPEAN PARLIAMENT AND OF THE COUNCIL of 4 April](#)).

The severity of all AEs will be graded according to the National Cancer Institute Common Toxicity Criteria for Adverse Event (NCI-CTCAE) on a five-point scale (Grade 1 to 5):

- Grade 1: Mild; asymptomatic or mild symptoms; clinical or diagnostic observations only; intervention not indicated.
- Grade 2: Moderate; minimal, local or non-invasive intervention indicated; limiting age-appropriate instrumental ADL¹.
- Grade 3: Severe or medically significant but not immediately life-threatening; hospitalization or prolongation of hospitalization indicated; disabling; limiting self-care ADL².
- Grade 4: Life-threatening consequences; urgent intervention indicated.
- Grade 5: Death related to AE.

The cause-effect relationship

The investigator has to assess in the AE form if the AE is related or not to the research, meaning:

- adverse event related to IMP
- adverse event related to study protocol i.e. related to:
 - o a procedure scheduled in the study protocol (i.e. exercise test, MRI, etc.), or
 - o a change or withdrawal of previous / concomitant treatment related to the conditions of the protocol or
 - o a product other than the IMP, taken as part of the protocol (NIMP or other);

Moreover, the investigator has to assess if the AE is related to disease progression. Cases ticked “related” by the investigator or judged by the sponsor as having a reasonable suspected causal relationship to the IMP (AE linked to the mechanism of action of the IMP...), will be considered as suspected Adverse Drug Reaction. In general, if a relationship between AE and IMP is at least reasonably possible (i.e. the relationship cannot be ruled out) it is to be considered as “related”.

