10.2. Statistical analysis

10.2.1. Safety Analysis

10.2.1.1. Adverse Events

Adverse events (AE) will be assessed according to the National Cancer Institute (NCI) Common Terminology Criteria Adverse Events (CTCAE) v5.0. Laboratory abnormalities will be classified into Common Terminology Criteria (CTC) grade according to CTCAE v5.0 and will be reported as adverse events.

Adverse events will be summarized in hierarchical tables, presenting the number and percentage of patients having at least one AE, and having at least one AE in each primary system organ class and for each preferred term using MedDRA coding, overall and at each dose level. AEs will be sorted by descending frequency, and alphabetically where frequency is tied. Such summaries will be produced for all AEs, serious adverse events (SAEs), grades 3 or 4 AEs, AEs leading to study treatment discontinuation, and AEs leading to dose-adjustment

or interruption of any of the drugs of the treatment. All of these summaries will be by system organ class, preferred term and, in some cases, maximum grade. Most of the summaries will be produced twice, once for all events regardless of study treatment relationship, and once for events suspected to be study treatment related. All deaths will be listed and summarized.

All adverse events will be listed, and any other information collected (e.g., start/end dates and duration of adverse event, severity or relatedness to study medication) will be listed as appropriate.

AEs of special interest will be summarized separately. All such events will be identified prior to database lock.

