3.5.1. Adverse Events

A treatment-emergent adverse event (TEAE) is defined as any untoward medical occurrence in a subject who received IMP (S95014), which occurs within the period from the Inclusion visit, until 30 days after the last S95014 infusion, or the date of withdrawal, whichever is earlier. TEAE will be assessed according to the National Cancer Institute (NCI) Common Terminology Criteria Adverse Events (CTCAE) v5.0. Clinically significant laboratory abnormalities will be classified into Common Terminology Criteria (CTC) grade according to CTCAE v5.0 and will be reported as adverse events if they are associated with signs and symptoms or, clinically significant in the investigator's opinion except if related to the disease, if they require curative therapies, if they induce change of study treatment administration. All analyses described below will be based on TEAEs, if not otherwise specified.

Adverse events will be summarized in hierarchical tables, presenting the number and percentage of subjects having at least one AE, and having at least one AE in each primary system organ class and for each preferred term using MedDRA coding. AEs will be sorted by descending frequency, and alphabetically where frequency is tied. Such summaries will be produced for all AEs, serious adverse events (SAEs), grades 3 or 4 AEs, AEs leading to study treatment discontinuation, and AEs leading to dose-adjustment or interruption of any of the drugs of the treatment. All of these summaries will be by system organ class, preferred term, starting dose level if applicable and, in some case, worst grade. Most of the summaries will be produced twice, once for all events regardless of study treatment relationship, and once for events suspected to be study treatment related. All deaths will be listed and summarized. All AEs will be listed, and any other information collected (e.g., start/end dates and duration of adverse event, severity or relatedness to study medication) will be listed as appropriate.

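### SAP 3.5.1 excepts disease-related laboratory abnormalities from the investigator's-opinion criterion for an adverse event; the supplied protocol has no such exception, and the gap is narrow

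*SAP*

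**What the plan says.** SAP 3.5.1 grades clinically significant laboratory abnormalities by CTCAE v5.0 and gives four routes by which one becomes an adverse event: signs and symptoms, the investigator's opinion, curative therapy, or an altered study treatment. From the second route on, the text reads "opinion except if related to the disease, if they require curative therapies, if they induce change of study treatment administration".

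The protocol covers the same ground in several places:

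- **8.2** opens its rule with "Abnormal laboratory values or test/exams results (i.e. blood pressure recording) will constitute an AE if they are" and gives five alternatives joined by *or*: symptoms; clinical significance as judged by the investigator; curative therapy; "associated with delay of study medication"; and study discontinuation. None mentions the disease.
- **8.3** includes among adverse events "an abnormal finding from an additional examination such as lab tests, X-rays, ECG, ...) which is deemed clinically relevant by the investigator". It also includes worsening of a condition present at entry, and names the studied disease as one such condition.
- **8.8** says of seriousness, severity and causality: "This evaluation must be assessed by the investigator and reported in the AE form". It adds: "Moreover, the investigator has to assess if the AE is related to disease progression".
- **8.1** says that a significant abnormality "must be reported on the adequate eCRF page by the investigator at each visit (AE, medical history or sign & symptoms").
- **10.2.1.1** says "Laboratory abnormalities will be classified into Common Terminology Criteria (CTC) grade according to CTCAE v5.0 and will be reported as adverse events", with no criterion attached.

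SAP section 6, reserved for changes from the planned analysis, is marked not applicable. SAP section 1 says that the plan follows protocol v1.0 and two non-substantial amendments, of May 2021 and January 2022.

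On severity, protocol 10.2.1.1 and SAP 3.5.1 both plan a summary of grade 3 and 4 events. The scale in protocol 8.8 ends at grade 5, death.

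**The concern.** Safety is the only objective with an analysis: protocol section 7 marks efficacy as not applicable, and the primary objective is continued access. The adverse-event tables are therefore the main output, and what counts as an event should be the same in both documents.

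The disease is leukaemia, and the laboratory panel in protocol Table (8.2) 1 includes blasts, platelets, haemoglobin and neutrophils. An investigator could reasonably attribute an abnormal value of any of these to the disease. So the exception concerns findings that can occur here.

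Under the protocol, such a finding is an adverse event if the investigator thinks it clinically significant, and its relation to disease progression is then recorded. Under the SAP, the same finding could be left out for that relation alone.

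**Working it through.** No figure in the plan is in dispute, so the check is a comparison of rules, followed by a bound on the effect.

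**1. The two rules.** For one abnormal value, let S = symptoms, C = clinically significant in the investigator's judgement, D = disease-related, T = needs curative therapy, L = delays study medication, X = leads to study discontinuation, and M = changes how study treatment is given.

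- Protocol 8.2: S or C or T or L or X.
- SAP 3.5.1, with the exception attached to the opinion criterion it follows: S or (C and not D) or T or M.

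**2. Are L and X covered by M?** A delay changes how treatment is given. Protocol 5.6.1 equates premature discontinuation of the product with premature discontinuation of the study. So M essentially covers both.

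**3. The difference.**

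- Counted by 8.2 and not by the SAP: C and D, with not S, not T and not M. This is one class.
- Counted by the SAP and not by 8.2: M without L or X, and not C, not S, not T. This is empty if a value that alters treatment is judged clinically significant. The SAP sentence starts from clinically significant abnormalities, which supports that assumption.

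**4. Does another protocol section supply the exception?** The 8.3 wording on laboratory findings has no disease carve-out, and its wording on worsening points the other way. Section 8.8 asks about disease progression for something that is already an adverse event. Section 8.9.1 sends events to medical history or to signs and symptoms only when they arise before the first administration and are not linked to a study procedure. After administration it requires all events up to the withdrawal visit. None of these supplies the exception.

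**5. Size.** The documents give no rate for the class in step 3. The effect of one patient on a percentage is at most 100/N.

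| N | Source | One patient |
|---|---|---|
| 88 | Planned number, protocol synopsis (approximate) | 1/88 = 1.14 points |
| 30 | Assumed equal split over three dose levels, 88/3 = 29.3 | 1/30 = 3.33 points |
| 29 | Same assumption | 1/29 = 3.45 points |

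Two patients give at most 2/88 = 2.27 points and three give 3/88 = 3.41 points. These are ceilings. A row counts patients with at least one event, so it changes only if the patient has no other event in that row. The number treated may differ from 88 and the dose-level sizes are not stated; a smaller N raises the ceiling.

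**6. Grade 5.** A summary of grades 3 and 4 covers two of the three grades from 3 upward. A patient whose only event of grade 3 or above is fatal does not enter it.

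**The case against.** **The sentence may do nothing.** The investigator decides on the form what is an adverse event. The SAP names no field or derivation for taking a recorded event out, and it plans summaries and a listing of all events. This stands in part: removal is possible and not demonstrated. But a rule placed in the analysis plan can be programmed, and if it has no effect there is no reason to keep it.

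**Protocol 8.1 offers a page that is not an adverse-event page, from consent to withdrawal.** That gives the exception some anchor. It is a recording option, though, and no section says that a disease-related finding after dosing ceases to be an adverse event.

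**An amendment may be the source.** The SAP rests on two amendments, and whether the exception came from one of them cannot be checked. If it did, section 6 would be correct. A reader might infer an undeclared departure from the protocol; the documents show only a conflict with the supplied text.

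**Other stronger readings.** The loose punctuation could suggest that all disease-related abnormalities are excluded, or even those needing therapy. Curative therapy and treatment effects are grounds for counting in 8.2, so the SAP list is best read the same way. A reader might also see a loss in the SAP's wording on treatment changes; step 2 of the working shows essentially none. Protocol 10.2.1.1 could be taken as making every abnormality an event, but it may be shorthand for 8.2.

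**Grade 5 is a layout choice.** Both documents agree on the table, and both list and summarise deaths. It is right that there is no contradiction.

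**Conclusion.** The conflict is real and minor. As supplied, the two documents differ on one class of laboratory finding: judged clinically significant, related to the disease, and meeting no other criterion. If the SAP rule is applied, events in that class leave the adverse-event tables although the protocol counts them.

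The number of patients is unknown and probably small. At the planned 88, one patient changes an overall row by no more than about 1.1 points. The any-event row is unlikely to move in children on multi-agent chemotherapy, so individual preferred-term rows are the more likely place. The values themselves remain visible in the shift tables and flagged listings of SAP 3.5.2, which do not depend on adverse-event status.

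This rests on three assumptions: the exception attaches only to the opinion criterion, a value that alters treatment is judged clinically significant, and the supplied protocol is the text in force.

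The grade 5 point is a separate improvement in table scope. It would be wrong to infer that deaths go unreported, since fatal events appear in the all-event, serious-event and death outputs. The gain is that a table likely to be read as severe or worse would include the most severe grade.

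**What to change.** 1. Delete the disease exception from SAP 3.5.1 and refer to protocol 8.2 as the single rule. If the exception is intended, justify it, say which recorded item identifies it, and declare it in SAP section 6 or cite the amendment that introduced it.
2. State in SAP 3.5.1 that the tables use adverse events as recorded by the investigator, with disease relation shown as an attribute.
3. Add a reference to 8.2 in protocol 10.2.1.1, so that it cannot be read as a rule without criteria.
4. Define the high-grade summary as grade 3 or higher (3 to 5) in both documents.

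The cost is minor rewording in the SAP and a protocol clarification, with no new data. Reported adverse-event counts may be slightly higher.

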8.9. Reporting procedures

8.9.1. Time frame for AE reporting

Any event meeting the above mentioned definitions (see sections 8.3 to 8.7) must be reported to the sponsor on an adverse event form if it occurred:

- before the first intake of the IMP for events related to the research
- at any time after the administration of IMP, up to the participant's withdrawal visit for all events,
- up to 30 calendar days after the participant's last intake of IMP for all ERIN, regardless of the supposed role of the research.
- irrespective of the time of onset after the end of the study in case of serious adverse event related to the research.

[figure not shown]
Of note, events occurring between the signature of the informed consent and the first administration of the test drug for which the investigator does not consider an association with

¹ Instrumental Activities of Daily Living (ADL) refer to preparing meals, shopping for groceries or clothes, using the telephone, managing money, etc.

² Self-care ADL refer to bathing, dressing and undressing, feeding self, using the toilet, taking medications, and not bedridden”.

any procedure/condition required by the study protocol must be reported as **medical history** or as signs and symptoms related to the studied disease in the dedicated form of the CRF.

For a given patient, medical histories and adverse events already reported in the initial CL2-95014-002 study will not be reported in the eCRF, except in case of worsening.

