6. CHANGES FROM THE PLANNED STATISTICAL ANALYSIS

Not applicable.

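### SAEs that the protocol collects after the SAP's treatment-emergent window closes enter no summary table unless fatal, and the SAP does not say whether its listing and death summary include them

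*SAP*

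**What the plan says.** **Collection.** Protocol 8.9.1 sets several reporting windows. All adverse events are reported up to the withdrawal visit. Events requiring immediate notification (ERIN), which under Protocol 8.7 include every SAE, are reported up to 30 calendar days after the participant's "last intake of IMP for all ERIN, regardless of the supposed role of the research". A further bullet extends reporting "irrespective of the time of onset after the end of the study in case of serious adverse event related to the research".

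**Analysis.** SAP 3.5.1 opens the TEAE window at the inclusion visit and runs it "until 30 days after the last S95014 infusion, or the date of withdrawal, whichever is earlier". It then sets the default: "All analyses described below will be based on TEAEs, if not otherwise specified". The tables by system organ class (SOC) and preferred term (PT) follow, including those for SAEs and for events suspected to be treatment related. The same section adds "All deaths will be listed and summarized" and "All AEs will be listed, and any other information collected", and does not say whether the TEAE default applies to these two outputs.

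**Protocol plan.** Protocol 10.2.1.1 describes the same set of tables without a treatment-emergent limit: "Such summaries will be produced for all AEs, serious adverse events (SAEs), grades 3 or 4 AEs". SAP section 6, headed "CHANGES FROM THE PLANNED STATISTICAL ANALYSIS", is marked not applicable.

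**The concern.** Safety is the only objective here with outcomes to analyse, since Protocol section 7 marks efficacy as not applicable. SAEs, above all those attributed to the research, are among the most informative data the study will hold. The protocol requires sites to report some of them after the TEAE window has closed, and the SAP then gives them no place in any count. A reader of the study report would see SAE and related-event tables and could reasonably take them to cover every SAE collected. The limit also narrows what Protocol 10.2.1.1 describes, and the SAP does not record that as a change.

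**Working it through.** **1. Windows side by side.** Day 0 is the last infusion. I take the SAP's date of withdrawal to be the withdrawal visit, which SAP 1.2.1 places no later than day 30; the SAP does not define the term.

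| Onset of a non-fatal SAE | Collected under Protocol 8.9.1 | In the SAP's TEAE tables |
|---|---|---|
| First infusion to withdrawal | Yes, any cause | Yes |
| After withdrawal, up to day 30 | Yes, any cause (as an ERIN) | No |
| After day 30, research-related | Yes, if the end of the study is read as the child's own end of study | No |
| After day 30, not related | No | No |

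The second and third rows are the gap.

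**2. Length of the gap before day 30.** With withdrawal on day w, the window ends at min(w, 30), so the part of the 30-day SAE collection left uncounted is 30 − min(w, 30):

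- w = 0: 30 days
- w = 7: 23 days
- w = 14: 16 days
- w = 21: 9 days
- w = 30: 0 days

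**3. Events after day 30.** SAP 1.2.1 puts the follow-up contact no earlier than day 30 and has adverse events recorded there. A scheduled contact therefore falls on or after the latest day the window can close. For example, a related SAE that starts on day 33 and is learned of in a call on day 35 would be recorded but would enter no SAE table.

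**4. Which outputs could still show the event.** A fatal late SAE enters the death summary if all deaths is read literally. A non-fatal one appears at most in the AE listing, if all AEs is read literally. No SAP summary table is specified for it.

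**5. Size.** The plan states no late-SAE rate, so there is no figure to reproduce. Assume that all of the approximately 88 planned children (Protocol synopsis) are treated. If k of them have an SAE that falls in the gap, the unreported proportion is k/88:

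- k = 0: 0% (exact 95% interval 0 to 4.11%)
- k = 1: 1/88 = 1.14% (0.03 to 6.17%)
- k = 2: 2/88 = 2.27% (0.28 to 7.97%)
- k = 3: 3/88 = 3.41% (0.71 to 9.64%)

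The chance of at least one such child is 1 − (1 − p)^88, where p is the risk per child. For assumed p of 0, 0.5%, 1%, 2% and 5% it is 0, 35.7%, 58.7%, 83.1% and 98.9%. The values of p are illustrative only.

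**The case against.** **A bounded TEAE table is sound.** The safety objective concerns the consolidation phase, and the protocol synopsis names TEAEs among the safety measures. The SAP's cut-off at withdrawal also matches the point to which Protocol 8.9.1 collects all adverse events, so the TEAE percentages rest on complete collection. This stands. It is a reason to leave the window alone and show the later SAEs separately.

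**The open-ended bullet is a reporting duty.** It sits under reporting procedures, and late events reach the sponsor's safety review under Protocol 8.9.3 whatever the SAP does. Protocol 4.1.1 defines the end of the trial as the last participant's last visit. On that trial-level reading the bullet applies only after the whole trial ends, and few events could arrive before database lock. This stands in part: it shrinks the gap after day 30 but does not touch the gap between withdrawal and day 30, which comes from the ERIN rule.

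**Research-related is not the same as S95014-related.** Protocol 8.8 counts study procedures and the backbone drugs (NIMPs) as part of the research, and backbone chemotherapy continues after withdrawal. A late research-related SAE need not belong in an S95014-related table. This stands, so any added table must show the attribution.

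**The templates may settle it.** The table and listing templates are in a separate document. They may show a post-treatment table or an unrestricted listing, but the SAP text does not say so.

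**Conclusion.** The point holds as a reporting gap. SAEs of any cause with onset between withdrawal and day 30, and research-related SAEs after that, are collected but enter no SAE or related-event table unless fatal. Even the fatal ones depend on how the death sentence is read. The limit departs from Protocol 10.2.1.1 without being declared. Each affected child is about 1.1 percentage points, assuming 88 treated. The number affected is unknown and may be zero.

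Three stronger readings are tempting, and the documents do not support them:

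- **That the related-SAE percentage is biased downward, or misses a given share of cases.** A count over a fixed window is not biased by events outside it, and any such share would need in-window and late event rates that the documents do not give.
- **That late events are shown nowhere at all.** The TEAE default allows exceptions, and the sentences on deaths and on listing all AEs may be two of them. The wording is ambiguous; omission is not proven.
- **That children who stop after one infusion lose most.** Their window opens at the inclusion visit and may close at withdrawal, so its length is not fixed at about 30 days, and nothing in the documents shows a larger loss for them.

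**What to change.** Add to SAP 3.5.1:

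> SAEs with onset after the TEAE window and entered before database lock (any causality up to day 30 after the last infusion; research-related thereafter) will be tabulated by SOC and PT in a separate post-treatment table, showing whether attributed to S95014 or to the protocol/NIMP, and listed. The listing of all AEs and the death summary are not restricted to TEAEs.

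Keep these events out of the TEAE percentages. Record in SAP section 6 that the AE tables are limited to TEAEs where Protocol 10.2.1.1 set no such limit.

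The cost is two SAP sentences, one table, a listing flag and one entry in section 6. The data are already required by Protocol 8.9.1, and no visit, treatment or existing percentage changes. The downside is that counts after day 30 come from passive follow-up of unequal length, so the new table should be read as a count of reported events and not as a rate.
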